- Lack of efficacy
- Adverse event
- Death
- Protocol deviation
- Physician decision
- Sponsor request
- Withdrawal by subject
- Lost to follow-up
- Other (specify). For example, pregnancy.

Subjects who require systemic corticosteroids or other non-study drug for treatment of their asthma should be considered to have lack of efficacy and withdrawn from study drug.

Subjects who meet one of the other protocol definitions of an asthma related event should also be considered to have lack of efficacy and be considered for withdraw from study drug. Instances where the Investigator feels that a subject meeting these criteria should continue receiving study drug should be discussed on a case-by-case basis with the medical monitor.

Subjects who are prematurely withdrawn from study drug should be followed up as instructed in the schedule of assessments.

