### 9.4 Treatments Administered

Eligible subjects will receive 600 mg AVTX-002 or placebo SC on Visit 2 (Day 0), Visit 5 (Day 28), and Visit 7 (Day 56).

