## 10.1 Study Duration

AVTX-002 and placebo treatment will be administered at Visit 2 (Day 0), Visit 5 (Day 28), and Visit 7 (Day 56). **A subject may not be dosed after Day 56.** The duration of the treatment period is considered 84 days, with each dose of study drug considered to be 28 days of treatment. The overall study period is approximately 135 days, including Screening and the 30-day, stabledose, run-in period.

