#### **12.3.4.1 Adverse Events**

Adverse event verbatim terms will be coded using the Medical Dictionary for Regulatory Activities (MedDRA). The overall incidence of subjects having at least one AE will be summarized by treatment group. The incidence of TEAEs will be summarized by treatment group, system organ class (SOC) and preferred term (PT). Each subject will be counted only once per SOC and preferred term. An AE will be considered treatment-emergent if it occurs after the first dose of investigational product and within 28 days after a subject's last dose of investigational product.

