10.5 Treatment Exposure

Based upon the PK of the study drug (halflife of 18.0 to 27.0 days) and dosage administered, each dose will count as 28 days of exposure to study drug. Therefore, days of exposure to study drug will be calculated as:

$$(last\ study\ drug\ dose\ date - first\ study\ drug\ dose\ date) + 28$$

A subject listing of treatment exposure will be presented, using the SAS, including the date and time of each study drug administration, reason for a dose not administered, location of each injection for each study drug administration, confirmation whether the injections were administered 4-10 cm from the umbilicus (with reason if not), and whether the complete dose was administered (with reason if not). The study drug exposure (days) will also be included in the listing.

Exposure to study drug (days) will be summarized by treatment group and overall using descriptive statistics, for the SAS. The number and percentage of subjects receiving 3, 2, 1, and 0 doses of study drug, respectively, will also be presented.

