10.7.1 Adverse Events

All AEs are collected from the time that the informed consent is signed until the end of study.

The definition for an AE to be considered treatmentemergent is as follows:

- If AE start time is recorded: an AE will be considered treatmentemergent if it occurs on or after the time of first dose of investigational product and within 28 days after a subject's last dose of investigational product.
- If AE start time is not recorded: an AE will be considered treatmentemergent if it occurs on or after the date of first dose of investigational product and within 28 days after a subject's last dose of investigational product.

Additionally, an AE that occurred prior to the date of first study drug dosing and increased in severity after start of first dosing and within 28 days of a subject's last dose of investigational product will also be considered treatment-emergent. An AE that occurred prior to first study drug dose and then again after first study drug dose at the same severity is NOT considered treatment-emergent.

AE verbatim terms will be coded to a SOC and PT using MedDRA, version 24, 01 Sep 2021.

For incidence of AEs by treatment group, SOC and PT, a subject will be counted only once per SOC and PT.

For AE incidence presented as the number and percentage of subjects with a specific AE, if there is more than one occurrence of an event, the event with the worst severity or the highest rated causality category will be summarized.

Summaries of AEs by SOC and PT will be sorted alphabetically for SOC, then by descending order of frequency of PT (for AVTX-002) within each SOC (then alphabetically for ties).

Summaries of AEs by PT will be sorted by descending order of frequency of PT (for AVTX-002), then alphabetically for ties.

Missing assessments of seriousness, intensity and relationship to study drug that have been queried and remain missing, will be treated 'worst case' for presentation filtering purposes as follows:

- Missing seriousness assessment: AE will be regarded as serious.
- Missing relationship to study drug: AE will be regarded probably related to study drug, except when start date is prior to first dose of study drug (in which case the AE will be regarded not related to study drug).
- Missing intensity assessment:
 - If subject has died, AE will be regarded Grade 5 intensity.
 - If subject has not died but subject had intervention indicated for the AE, AE will be regarded Grade 4 intensity.

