 - If none of the previous conditions are met, AE will be regarded Grade 3 intensity.

The following subject listings will be provided, using the SAS:

- All AEs (including TEAEs and nonTEAEs)
- All serious AEs (including serious TEAEs and serious nonTEAEs)
- All AEs leading to death
- All AEs leading to discontinuation of study drug

An overall summary of AEs will be provided, containing the number and percentage of subjects by treatment group with:

- any AEs
- any serious AEs
- any TEAEs
- any study drug related TEAEs

- any TEAEs leading to study drug discontinuation
- any study drug related TEAEs leading to study drug discontinuation
- any TEAEs by maximum CTCAE grade (Grade 1, Grade 2, Grade 3, Grade 4, Grade 5)
- any serious TEAEs
- any study drug related serious TEAEs
- any TEAEs leading to death
- any serious TEAEs by maximum CTCAE grade (Grade 1, Grade 2, Grade 3, Grade 4, Grade 5)

The following summary tables will be provided by SOC and PT, by treatment group:

- Incidence of TEAEs
- Incidence of study drug related TEAEs
- Incidence of TEAEs leading to study drug discontinuation.
- Incidence of study drug related TEAEs leading to study drug discontinuation
- Incidence of TEAEs by maximum CTCAE grade (Grade 1, Grade 2, Grade 3, Grade 4, Grade 5)
- Incidence of serious AEs (only if incidence of serious AEs and serious TEAEs differs)
- Incidence of serious TEAEs
- Incidence of study drug related serious TEAEs
- Incidence of serious TEAEs by maximum CTCAE grade (Grade 1, Grade 2, Grade 3, Grade 4, Grade 5)

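### TEAEs are tabulated only as crude percentages, although efficacy-driven withdrawal can shorten the TEAE window more often on placebo

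*SAP*

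**What the plan says.** - **AE display.** SAP 10.7.1: "An overall summary of AEs will be provided, containing the number and percentage of subjects by treatment group with" a list of AE and TEAE categories, followed by incidence tables by SOC and PT. Protocol 12.3.4.1 plans the same kind of incidence summary. Neither lists an exposure-adjusted rate, a time-to-first-TEAE analysis or a common-window table.
- **TEAE window.** A TEAE starts on or after first dosing and "within 28 days after a subject's last dose of investigational product" (SAP 10.7.1). A pre-existing AE that worsens in that period also counts.
- **Dosing and exposure.** Doses are given on Days 0, 28 and 56 (Protocol 9.4). Protocol 10.1 adds: "The duration of the treatment period is considered 84 days, with each dose of study drug considered to be 28 days of treatment". SAP 10.5 agrees that "each dose will count as 28 days of exposure to study drug". It tabulates exposure days, and the numbers receiving 3, 2, 1 and 0 doses, apart from the AE tables.
- **Withdrawal.** Under Protocol 8.7, subjects who need systemic corticosteroids or another non-study drug for their asthma "should be considered to have lack of efficacy and withdrawn from study drug". Those meeting another event criterion are to "be considered for withdraw from study drug", and continuation is discussed case by case. Protocol 10.2.2.1 requires withdrawal from the study once background or alternate therapy is started.
- **Follow-up.** After discontinuation, the early termination visit falls 4 weeks after the last dose (Protocol Table 1, footnote 2), so follow-up matches the TEAE window.
- **AE recording.** Non-serious events that meet the asthma-event definition need not be recorded as AEs. Exacerbations that fall short of it are recorded (Protocol 11.1.1).

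**The concern.** The length of time in which a subject can contribute a TEAE depends on how many doses were given, and that number depends on efficacy. A subject who stops after one or two doses has 28 or 56 days in which to report a TEAE. A subject with three doses has 84. If the drug prevents asthma events, more of the early stoppers are on placebo. With equal underlying TEAE risk, the placebo percentage is then pulled down further than the AVTX-002 percentage.

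Safety and tolerability is the first secondary objective (Protocol 7.1.2), and readers will compare the two columns even though no test is planned. The SAP already divides by days of participation for the annual asthma-event rate (SAP 6.2.1), but has no counterpart for safety.

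**Working it through.** **Inputs from the documents.** Doses on Days 0, 28 and 56; TEAE window to last dose + 28 days; planning event rates of 44% on placebo and 6% on active, with ranges 30–50% and 5–8%; 40 subjects per arm (Protocol 12.1).

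**Assumptions, not in the documents.** A constant TEAE hazard, equal in both arms and unrelated to asthma events, giving 40% over 84 days; dosing stops at the asthma event; all other subjects receive three doses; event days spread evenly over a stated range.

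**1. The plan's own figures.** Treatment period: (56 − 0) + 28 = 84 days, as stated. Power for 44% v 6% at 40 per arm, two-sided 5% (sidedness assumed), pooled variance under the null:

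z = (0.38√40 − 1.96√(2 × 0.25 × 0.75)) / √(0.44 × 0.56 + 0.06 × 0.94) = (2.403 − 1.200) / 0.550 = 2.19, so power is 98.6%.

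This agrees with the stated figure of over 95%.

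**2. TEAE incidence by doses received.** Incidence = 1 − 0.6^(window/84).

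| Doses | Window (days) | Incidence |
|---|---|---|
| 1 (event before Day 28) | 28 | 15.7% |
| 2 (event Days 28–56) | 56 | 28.9% |
| 3 (event later, or none) | 84 | 40.0% |

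**3. Crude incidence by arm.** Let I be the average incidence in event subjects. Arm incidence = 40% − (event rate) × (40% − I), so the gap = 0.38 × (40% − I). Mean windows follow in the same way.

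| Event days | Share with 1 / 2 / 3 doses | I | Mean window, AVTX-002 v placebo | Crude TEAE, AVTX-002 v placebo | Gap (points) |
|---|---|---|---|---|---|
| 14–98 | 1/6, 1/3, 1/2 | 32.2% | 82.9 v 75.8 | 39.5% v 36.6% | 3.0 |
| 14–56 | 1/3, 2/3, 0 | 24.5% | 81.8 v 67.6 | 39.1% v 33.2% | 5.9 |
| 42–98 | 0, 1/4, 3/4 | 37.2% | 83.6 v 80.9 | 39.8% v 38.8% | 1.1 |
| All after 56 | 0, 0, 1 | 40.0% | 84 v 84 | 40% v 40% | 0 |
| All before 28 (extreme) | 1, 0, 0 | 15.7% | 80.6 v 59.4 | 38.5% v 29.3% | 9.3 |

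**4. Sensitivity.**
- If half the events stop dosing, the first three gaps become 1.5, 3.0 and 0.5 points.
- Across the planning range, with events over Days 14–98: 8% v 30% gives 0.22 × 7.8 = 1.7 points; 5% v 50% gives 0.45 × 7.8 = 3.5 points.
- With TEAE risk 50% instead of 40%, 6% v 44% and Days 14–98, the gap is 3.5 points.
- For a single PT with 5% incidence, the first three timing patterns give 0.2 to 0.8 points, about 0.06 to 0.33 of a subject in 40.
- For scale, the 95% half-width for a difference at 40% and 40 per arm is 1.96√(2 × 0.4 × 0.6 / 40) = 21.5 points.

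**5. Would time-at-risk displays remove it?** Under the same assumptions the first-event rate is −ln(0.6)/12 weeks = 4.26 per 100 subject-weeks in both arms. A common Day 0–28 window gives 15.7% in both. Rates can also mislead, however. Suppose 20% of subjects in each arm have a TEAE at Day 3 and none occur later. The rate is 0.2 / (0.2 × 3 + 0.8 × mean window). With the windows above, the placebo rate is then 9% higher (Days 14–98) or 21% higher (Days 14–56), with no true difference.

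**The case against.** A reader might infer that AVTX-002 will look less safe than it is if it works, across every SOC and PT row. The documents do not support that, for these reasons:

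- **Only stops before the third dose matter.** Fluticasone is not fully withdrawn until Day 42, so many events may come after Day 56, with no effect on the window.
- **Withdrawal from study drug is not automatic.** For several event criteria it is a case-by-case decision (Protocol 8.7).
- **TEAEs starting in the first 28 days are unaffected.** Only later onsets can be lost.
- **An opposing force exists.** Exacerbations below the event definition, and qualifying events that are serious, are recorded as AEs (Protocol 11.1.1). An effective drug should leave more of both on placebo. In the Days 14–98 case the gap is 3.0 points, or 1.2 subjects in 40, so one or two placebo subjects whose only TEAE is an asthma AE would cancel it. The net effect cannot be computed from the documents.
- **The size is small and the imbalance is visible.** The gap is well inside sampling error, safety is descriptive (SAP 10.7), and SAP 10.5 tabulates exposure by group. The AVTX-002 percentage itself barely moves.

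All of this stands as a limit on the claim. It does not remove the point: the exposure table reveals an imbalance but corrects no AE row, and a shift that grows with efficacy is not covered by a confidence interval. The warning in step 5 also stands. Basing between-arm statements on rates alone could hide early harm.

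**Conclusion.** The point holds in a limited form. For later-onset TEAEs, crude percentages may understate placebo incidence relative to AVTX-002 if the drug works and asthma events stop dosing before the third dose. The likely size is about 1 to 6 points under the planning rates, equal constant hazards (40% over 84 days) and withdrawal at every event. It is about half that if half the events stop dosing, and zero for events after the third dose. A gap above 9 points needs every event before Day 28. For any TEAE the net direction is uncertain, so a prediction that the drug will look less safe would go beyond the documents. This is a modest gap in the safety reporting that is cheap to close; it does not invalidate the safety analysis.

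**What to change.** Keep the crude percentages in SAP 10.7.1. Add one supplementary table by treatment group for any TEAE, serious TEAEs, related TEAEs and common PTs, with two parts:

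1. Time-at-risk-adjusted results with 95% confidence intervals. Use either first-event rates per 100 subject-weeks or Kaplan–Meier cumulative incidence of first TEAE. Time runs from first dose to first onset, end of the TEAE window or last contact, whichever comes first.
2. Incidence in a common Day 0–28 window as companion.

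State that between-arm differences will be interpreted from the crude and adjusted displays together, not from the rates alone.

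The cost is one more table from dates already collected. Rates assume a roughly constant hazard. Kaplan–Meier does not, but both treat withdrawal as unrelated to TEAE risk.

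Separately, Protocol 8.7 speaks of withdrawal from study drug, while 9.11.4 and 10.2.2.1 speak of withdrawal from the study. These passages should be reconciled so that the end of follow-up is unambiguous.

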10.7.2 Clinical Laboratory Values

Subject listings, using the SAS, will be provided for all clinical laboratory tests, ie, hematology, clinical chemistry, urinalysis, and pregnancy tests.

Observed values of hematology and clinical chemistry parameters, and continuous urinalysis parameters (SG, pH) at selected time points, and change from baseline in these parameters at each post-baseline time point, will be summarized descriptively by treatment group. The overall worst value post-baseline (which includes results from unscheduled visits) will also be included in the summaries. Table 10 provides the directionality of the worst values for each laboratory parameter.

Shift tables for hematology and clinical chemistry laboratory parameters, using laboratory CTCAE version 5.0 grading (see Table 9) showing changes from baseline to post-baseline values will be summarized using counts and percentages. For a specific laboratory parameter, subjects with both baseline and a post-baseline value will be included for shift summaries. For computing percentages, the denominator will be the total number of subjects with non-missing baseline and post-baseline values for the respective post-baseline visit point and treatment group.

The number and percentage of subjects meeting criteria for abnormal LFTs (see [Table 6](#)) will be summarized by treatment group and time point (including results from unscheduled visits). For computing percentages, the denominator will be the number of subjects with a post-baseline value for the specific laboratory parameter and the respective time point. Only subjects with newly occurring values (at least one post-baseline measurement meeting the criterion but not meeting the criterion at baseline) will be counted.

The number and percentage of subjects meeting PCI criteria for laboratory values (see [Table 7](#)) post-baseline will be presented by treatment group (including results from unscheduled visits). For computing percentages, the denominator will be the number of subjects with a post-baseline value for the specific laboratory parameter and time point; the exception is for hemoglobin where the denominator will be the number of subjects with both a baseline and a post-baseline value at the respective time point, given that the criteria for hemoglobin includes both an absolute value as well as change from baseline criteria. Only subjects with newly occurring values (at least one post-baseline measurement meeting the criterion but not meeting the criterion at baseline) will be counted. Subjects with laboratory values meeting PCI criteria will be included in a subject listing; all values for the laboratory parameter meeting PCI criteria will be included in the listing.

For results reported as not fully numeric (eg, result is reported as < 3.5 mmol/L), the numeric portion of the result (ie, 3.5 in this case) will be used in case calculations/derivations need to be performed (eg, when summary statistics or change from baseline values are calculated, or toxicity grading is derived).

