### **8.5 Study Entry Criteria**

Subjects are to be enrolled based on the inclusion and exclusion criteria below. The diagnosis of NEA is determined at Screening Visit 1 based upon Inclusion Criteria 2 through 5. At Baseline Visit 2, a review of all Inclusion/Exclusion criteria should be done to ensure continued eligibility prior to randomization and dosing the subject. As long as the subject qualifies as having NEA per protocol at the Screening Visit, there is no expectation that their diagnosis be re-confirmed at Baseline Visit 2, and therefore changes in eosinophil count and/or ACQ score within the period of time between Screening Visit 1 and Baseline Visit 2 would not reverse their diagnosis and would not disqualify the subject.

Although chemistry and hematology labs must be drawn as part of Baseline Visit 2 procedures,

there is not an expectation that these test results be available during the visit to re-confirm eligibility (Exclusion Criteria 12 and 13).

Per the schedule of assessments, a urine pregnancy test must be completed and show negative results at Baseline Visit 2 prior to randomization and dosing. Subjects with a positive urine pregnancy test should NOT be randomized and dosed with AVTX-002.

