### **8.5.2 Exclusion Criteria**

The presence of any of the following criteria excludes a subject from the study:

1. Pulmonary disease other than asthma.
2. Currently on biologic therapy. Previous biologic therapy is permitted with adequate washout(12 weeks or 5 half-lives, whichever is longer).

3. Subjects who:
  - Are current smokers, users of inhaled cannabis and/or e-cigarettes/vaping devices or,
  - Have a history of smoking  $>/=10$  pack years or,
  - Have a history of inhaled cannabis  $>4$  days/week for the most recent 3 months prior to screening or,
  - Use e-cigarettes or vaping devices  $>4$  days/week for the most recent 3 months prior to screening.
4. Current suspected drug or alcohol abuse.
5. Use of systemic immunosuppressants within the last 6 months.
6. Use of systemic corticosteroids within 6 weeks prior to Screening or use of antibiotics within 4 weeks prior to Screening.
7. Subjects that are pregnant or breastfeeding.
8. Subject has a history of neoplasia (except for a curatively treated non-melanoma skin tumor or carcinoma of the cervix treated in situ with no indication of recurrence) within the 10 years prior to Visit 1.
9. Subject has a chronic, active infection or another disease, which entails a tendency towards infection.
10. Subject has a chronic severe or uncontrolled medical disorder that might confound the results of safety assessments conducted in this study.
11. Subject has a history of unresolved latent tuberculosis.
12. Subject has alanine aminotransferase (ALT)/ aspartate aminotransferase (AST)  $>5$  upper limit of normal (ULN) and/or serum creatinine concentration  $>1.5$  mg/dL.
13. Subject has hemoglobin  $\leq 10$  g/dL, neutrophils  $\leq 1,500/\mu\text{l}$ , and/or platelets  $\leq 75,000/\mu\text{l}$ .
14. Subject has received a live vaccine within 12 weeks prior to Visit 2.
15. Subject has used an investigational product, including Emergency Use Authorization (EUA) vaccines, within 30 days of Visit 1.
16. Subject has known or suspected intolerance or hypersensitivity to the investigational product(s), closely related compounds, or any ingredients of the investigational product.
17. There is any concern on the part of the investigator regarding the subject's safety, compliance, or suitability with respect to his/her participation in the study.

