6.1.1 Justification of Sample Size

The sample size in this study will be approximately 80 subjects, ie, 40 subjects per treatment arm, randomized in a 1:1 ratio.

The sample size estimate was based on the estimated proportions of subjects in the 2 treatment groups expected to have an asthma related event as defined by the primary endpoint. In a study of similar design with another asthma controller therapy, rates of 6% in the active group and 44% in the placebo group were observed [3]. If these estimates were used as is, then a study with 40 subjects per group would have over 95% power. Considering likely variations from the cited study, estimates of sample were assessed assuming a Type I error of 5% and the proportion of subjects with an asthma related event ranging from 30% to 50% in the placebo group and 5% to 8% in the active group. In the 20 such scenarios examined, only in the cases in which the difference between treatments gets below 23% does the power fall slightly below 80%. In the vast majority of cases examined the power is greater than 90%.

The overall event rate may be assessed in a blinded fashion when an adequate amount of subject followup has occurred. If this event rate is found to be much lower than assumed, a sample size reestimation may be performed.

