9.2 Baseline and Related Changes Definition

In general and unless otherwise specified, baseline is defined as the last available assessment prior to the first dose of the study drug.

CFB is calculated as: $CFB = observed\ value - baseline\ value$

CFB% is calculated as: $CFB\% = \left(CFB / \text{baseline value} \right) \times 100$ (if the baseline value is 0, CFB% cannot be calculated)

Where unscheduled/repeat assessments are relevant and exist for any subject at a particular visit they will also be considered in the baseline definitions, provided they remain prior to the first dose of study drug.

Visit 1a (Day 7 [2 days]) with diary activation was added to the protocol Schedule of Assessments in Protocol Version 4.0 (Amendment 3), 05 May 2022. Therefore, subjects enrolled prior to this amendment did not have a diary activated until the day of randomization (ie, they will not have diary entries during the 7 days preceding Visit 2). A baseline value cannot be calculated for subjects with no diary entries before the day of randomization. To include such subjects in analyses, additional definitions of baseline have been included in which Day 1 entries or Day 1 through Day 7 entries may be used for calculation of baseline when a subject does not have sufficient diary entries prior to Day 1. This approach has been taken given that all subjects have received a 30day regimen of stable asthma medications leading up to Day 1 which will be maintained until Day 14 per protocol; therefore, a Day 1 (or Day 1 through Day 7) diary entry is a reasonable representation of their baseline. The baseline definitions are detailed below for each of the following subject diary assessments:

Asthma Symptom Diary Assessment	Baseline Definition

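### SAP 10.7.2 counts only newly occurring laboratory abnormalities but keeps subjects who already met the criterion at baseline in the denominator, so some new-onset percentages come out slightly too low

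*SAP*

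**What the plan says.** SAP 10.7.2 gives two summaries of abnormal laboratory values, each as a number and percentage of subjects by treatment group.

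- **Abnormal liver tests (Table 6).** Denominator: "the denominator will be the number of subjects with a post-baseline value for the specific laboratory parameter and the respective time point". Numerator: "Only subjects with newly occurring values (at least one post-baseline measurement meeting the criterion but not meeting the criterion at baseline) will be counted".
- **Potentially clinically important values (Table 7).** Denominator: "the denominator will be the number of subjects with a post-baseline value for the specific laboratory parameter and time point". The numerator rule is repeated in the same words.

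There is one exception in the Table 7 paragraph: "the exception is for hemoglobin where the denominator will be the number of subjects with both a baseline and a post-baseline value". The SAP's reason is that the hemoglobin criterion contains a change from baseline. The exception does not remove subjects who met a criterion at baseline.

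Under SAP 9.2, unless otherwise specified, "baseline is defined as the last available assessment prior to the first dose of the study drug". A screening result can therefore serve as baseline if the Visit 2 result is missing.

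**The concern.** The numerator and the denominator describe different groups. The numerator can contain only subjects who were free of the abnormality at baseline. The denominator contains everyone tested after baseline, including those who already had it. A percentage printed beside a count of newly occurring cases will be read as the risk of developing the abnormality, and it is not quite that.

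The error runs one way: the percentage can be too low as a new-onset rate, never too high. If the arms differ in how many subjects were positive at baseline, the comparison between them also shifts a little. These are the tables a reader consults for liver and laboratory signals.

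**Working it through.** The documents state no figure for these percentages, so there is none to reproduce. Two questions need checking: whether subjects can meet a criterion at baseline, and how much it matters if they do.

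**1. Who can be positive at baseline?** Set the entry limits (Protocol 8.5.2, exclusions 12 and 13) against SAP Tables 6 and 7.

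| Criterion | Entry limit | Positive at baseline? |
|---|---|---|
| ALT/AST > 3 x ULN | excluded only above 5 x ULN | possible (above 3, up to 5 x ULN) |
| ALT/AST > 5 and > 10 x ULN | excluded above 5 x ULN | unlikely |
| Bilirubin, sodium, potassium, leukocytes, lymphocytes, high platelets | no numeric limit | possible |
| Neutrophils < 1.0 x 10⁹/L | excluded at 1,500/µL or below | unlikely |
| Platelets ≤ 75 x 10⁹/L | excluded at 75,000/µL or below | unlikely |
| Creatinine > 150 µmol/L | excluded above 1.5 mg/dL, about 1.5 x 88.4 = 132.6 µmol/L (conversion factor assumed) | unlikely |
| Hemoglobin | criterion requires a change from baseline | no |

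The entry says unlikely rather than impossible because a value can drift between screening and Visit 2. Protocol 8.5 says of the Visit 2 chemistry and hematology that "there is not an expectation that these test results be available during the visit to re-confirm eligibility".

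**2. Size of the effect.** Let n be the subjects with a post-baseline value, b those of them who met the criterion at baseline, and x the newly occurring cases.

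- SAP percentage = x / n
- New-onset percentage = x / (n − b)
- Ratio of the two = (n − b) / n = 1 − b/n

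The relative understatement is therefore b/n. SAP 6.1.1 plans 40 subjects per arm, so take n = 40. The documents do not give b; the table shows an assumed range.

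| b | b/n | x = 2: SAP → at risk | x = 4: SAP → at risk |
|---|---|---|---|
| 0 | 0% | 5.00% → 5.00% | 10.00% → 10.00% |
| 1 | 2.5% | 5.00% → 5.13% | 10.00% → 10.26% |
| 2 | 5% | 5.00% → 5.26% | 10.00% → 10.53% |
| 4 | 10% | 5.00% → 5.56% | 10.00% → 11.11% |
| 8 | 20% | 5.00% → 6.25% | 10.00% → 12.50% |

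At later visits n may be below 40, and b/n is then larger for the same b. The documents give no retention figure from which to put a number on this.

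**3. Arm comparison.** Suppose the true new-onset risk is 10% in both arms, with b = 4 in one and b = 0 in the other.

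- Arm with b = 4: expected SAP percentage = 10% x 36/40 = 9.0%
- Arm with b = 0: expected SAP percentage = 10% x 40/40 = 10.0%

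With the milder imbalance of b = 2 against b = 1, the figures are 9.5% (10% x 38/40) and 9.75% (10% x 39/40).

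**The case against.** **It is a reporting convention.** The SAP promises a number and percentage of subjects and never calls the result a new-onset risk. The share of all tested subjects who show a new abnormality is a coherent quantity, and the treatment-emergent adverse event tables are built in a similar way. It stands that relabelling would make the present percentage correct. It does not remove the mismatch: the SAP asks for a baseline value for hemoglobin because that criterion refers to baseline, and the newly-occurring rule makes every row refer to baseline.

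**Baseline status is shown elsewhere.** SAP 10.7.2 also requires CTCAE shift tables restricted to subjects with both values, listings of all laboratory results, and a listing of subjects meeting the Table 7 criteria. Many grade boundaries in Table 9 coincide with the cut-points here, for example ALT/AST at 3 x ULN, bilirubin at 1.5 x ULN and potassium at 5.5 and 3.0 mmol/L. This largely stands and is a main reason the point is minor. Cover is incomplete: high platelets, and leukocytes at 16.0 x 10⁹/L, have no matching grade boundary.

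**Stronger readings that the documents do not support.**

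- A reader might infer that only subjects with normal baseline values can be counted. The rule is failure to meet the specific criterion; a subject with a mildly raised baseline ALT can still enter the numerator.
- A reader might infer that every percentage in these tables is too low. Where b = 0 there is no effect.
- A reader might infer that subjects without a baseline value add much to the denominator. Screening laboratory tests are scheduled and can serve as baseline, so this group should be almost empty.
- A reader might infer that no rule limits entry with abnormal bilirubin, electrolytes or blood counts. Where no numeric limit applies, the general exclusions for infection, uncontrolled disease and investigator concern (items 9, 10 and 17) may still remove some of these subjects.

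**Conclusion.** The mismatch is explicit in both paragraphs of SAP 10.7.2. For the rows where baseline-positive subjects can enrol, the reported percentage is too low as a new-onset rate by the factor 1 − b/n whenever b is at least 1 and new cases occur. With 1 to 4 of 40 positive at baseline the relative shortfall is 2.5% to 10%, at most about one percentage point at a 10% rate. These values of b are assumptions, and an imbalance of 4 against 0 would be extreme.

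The wording defect is certain; a material understatement is not shown. A reader might go further and conclude that a safety signal could be hidden. The documents do not support that: counts stand beside the percentages, SAP 10.7 plans no formal safety inference unless otherwise noted, and individual values are listed. It is a minor correction.

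**What to change.** In both paragraphs of SAP 10.7.2, define the denominator separately for each criterion: subjects with a non-missing baseline value that does not meet that criterion and with a post-baseline value at the time point. Beside each row, show the number of tested subjects who already met the criterion at baseline. The hemoglobin exception is then covered by the general rule.

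If a common denominator is preferred, keep the present one and label the percentage as a share of all subjects tested.

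The cost is two SAP sentences and a denominator flag in the programs, with no new data. The small drawback is that denominators will differ between rows of one parameter, for instance ALT above 3, 5 and 10 x ULN, so each row must print its own.
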